9.2 Demographics and Subject Disposition

Subject disposition will be listed. The demographic variables age, sex, ethnicity, race, height, weight and body mass index (BMI) will be summarized and listed.

9.3 Pharmacokinetic Assessment

9.3.1 Pharmacokinetic Analysis

Insulin lispro PK parameter estimates for LY900014 will be calculated using standard noncompartmental methods of analysis.

Free serum insulin lispro concentrations will be used to calculate several PK parameters, including maximum observed drug concentration (C_{max}), time of maximum observed drug concentration (t_{max}), $t_{1/2}$, and area under the concentration versus time curve from time zero to time t, where t is the last time point with a measurable concentration (AUC[0- t_{last}]), AUC from time zero to 10 hours (AUC[0-10h]), area under the concentration versus time curve from time zero to infinity (AUC[0- ∞]), apparent total body clearance of drug calculated after extra-vascular administration (CL/F), and apparent volume of distribution during the terminal phase after extra-

vascular administration (V_z/F) will be determined. In addition, the total body clearance of drug calculated (CL), and volume of distribution (V) after IV administration also will be determined. Other parameters may be calculated as deemed appropriate. Additional partial AUCs may be computed as necessary.

Additional model-based analysis will be conducted as deemed appropriate to describe the elimination and absorption profiles.

Given the predicted low systemic concentrations of treprostinil, the PK analysis of treprostinil from the IV LY900014 dosing will be conducted using the available data. The primary analysis of the treprostinil concentrations will be focused on assessing t_{max} and C_{max} .

Although attempts will be made to adhere to the scheduled collection times (Section 2), it is recognized that situations arise that may compromise the scheduled times. Parameters will be individually calculated for each subject based on actual collection times and presented using summary statistics.

The absolute bioavailability will be calculated using the ratio of the insulin lispro AUC(0-∞) following injection into the thigh, abdomen, and deltoid to the insulin lispro AUC(0-∞) following IV administration. A table of these percent absolute bioavailabilities will be presented.

9.3.2 Pharmacokinetic Statistical Methodology

Log-transformed AUC(0-∞) and C_{max} for insulin lispro will be evaluated to estimate geometric least-squares means (LSmeans), ratios of geometric LSmeans between injection sites (deltoid and thigh compared with the abdomen), and their corresponding 90% CIs using the statistical model that includes injection site, period, and sequence as fixed effects, and subject within sequence as a random effect. Data from the deltoid, thigh and abdomen injection sites will be included in the same model. The primary parameter for the statistical analysis of the relative bioavailability between injection sites will be the AUC(0-∞).

Example SAS Code:

```
proc mixed data=pk;
class subject site period sequence ;
model logpk = site period sequence / ddfm=kr;
lsmeans site / pdiff=control('abdomen') alpha=0.1;
random subject(sequence);
run;
```

The analyses will also be performed using all available data and repeated using the subset of the subjects who complete all treatment periods with evaluable data.

9.4 Glucodynamic Assessment

9.4.1 Glucodynamic Analysis

Glucodynamic assessments will be determined from the glucose clamp procedure, where the GIR over time will be used as a measure of insulin effect. Glucodynamic analyses will be conducted on those subjects who complete at least 1 clamp procedure.

A locally weighted scatterplot smoothing (LOESS) function will be applied to all individual GIR versus time profiles in each treatment group and age group using CCI. The fitted data for each subject will be used to calculate the following GD parameters: maximum GIR (R_{max}), time to R_{max} (tR_{max}), and total amount of glucose infused (G_{tot}). Additional GD parameters, may be computed as necessary. The values of these GD parameters will be summarized by treatment group through descriptive statistics. Mean LOESS fits of GIR versus time profiles will be generated.

9.4.2 Glucodynamic Statistical Methodology

Log-transformed R_{max} and G_{tot} will be evaluated to estimate geometric LSmeans, ratios of geometric LSmeans between injection sites (deltoid and thigh compared with the abdomen), and their corresponding 90% CIs using the statistical model that includes injection site, period, and sequence as fixed effects, and subject within sequence as a random effect. Data from the deltoid, thigh and abdomen injection sites will be included in the same model. For GD parameters that have at least 1 subject with a value equal to zero, a value equal to the smallest non-zero observed GD value for that parameter divided by 2 will be added to all values, and the analysis of the log-transformed data will be performed. In addition, as a sensitivity analysis, a nonparametric analysis will be performed for that parameter based on the original parameters using a Wilcoxon Signed Rank test. Similar SAS code to that used to analyze the PK parameters will be used to analyze the GD parameters.

The analyses will also be performed using all available data and repeated using the subset of the subjects who complete all treatment periods with evaluable data.

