### Rationale:

In clinical practice, it is recommended that patients rotate insulin injections and may inject insulin at different tissue sites. The actual site of subcutaneous (SC) injection may influence the absorption pharmacokinetics (PK), as well as, the glucodynamic (GD) effect. The primary objective of this study is therefore to compare the bioavailability of insulin lispro following administration of the commercial formulation of LY900014 at 3 different injection sites SC in the abdominal wall, thigh, and deltoid. In addition, the intravenous (IV) administration will serve as the reference to determine the absolute bioavailability of SC injections into the deltoid, thigh or abdomen and GD activity.

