### 3. Introduction

#### 3.1. Study Rationale

In clinical practice, it is recommended that patients rotate insulin injections and may inject insulin at different tissue sites. The actual site of subcutaneous (SC) injection may influence the absorption pharmacokinetics (PK), as well as, the glucodynamic (GD) effect. The primary objective of this study is therefore to compare the bioavailability of insulin lispro following administration of the commercial formulation of LY900014 at 3 different injection sites SC in the abdominal wall, thigh, and deltoid. In addition, the intravenous (IV) administration will serve as the reference to determine the absolute bioavailability of SC injections into the deltoid, thigh, or abdomen and GD activity.

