##### **10.3.3.2. Glucodynamic Statistical Inference**

Log-transformed Rmax and Gtot will be evaluated to estimate geometric LSmeans, ratios of geometric LSmeans between injection sites (deltoid and thigh compared with the abdomen), and their corresponding 90% CIs using the statistical model that includes injection site, period, and sequence as fixed effects, and subject within sequence as a random effect. For GD parameters that have at least 1 subject with a value equal to zero, a value equal to the smallest non-zero observed GD value for that parameter divided by 2 will be added to all values, and the analysis of the log-transformed data will be performed. In addition, as a sensitivity analysis, a nonparametric analysis will be performed for that parameter.

The analyses will also be performed using the subset of the subjects who complete all treatment periods with evaluable data.

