4.2 Secondary Objectives

- To evaluate the tolerability of LY900014 in healthy subjects.
- To evaluate the GD during euglycemic clamp procedure of LY900014 after SC injection into the abdomen, thigh, and deltoid and IV in healthy subjects.

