5. STUDY DESIGN

This is a Phase 1, single-center, open-label, 4-period, randomized, crossover, up to 10-hour euglycemic clamp study in approximately 28 healthy subjects to compare the insulin lispro PK and GD of LY900014 after SC administration of a 15-U dose at 3 different injection sites and a single IV bolus injection of 15 U. The SC injection sites are the abdomen, thigh, and deltoid.

Subjects will be required to attend the clinical research unit (CRU) on at least 6 occasions:

- screening visit (may occur up to 28 days before randomization)
- four treatment visits for the clamp procedure (study Periods 1 to 4) with a wash-out period of ≥ 3 days between discharge and the next admission to the CRU
- follow-up visit (at least 14 days after last dose), or early discontinuation.

Each subject will be randomly assigned to a treatment sequence and will be administered single doses of 15 U of LY900014 (on 4 occasions).

Subjects will be admitted to the CRU on the evening before each dosing day and will remain in the CRU for the duration of the clamp period and until discharge by the investigator. Subjects are expected to fast for at least 8 hours before each dose. Following dose administration, each subject will undergo a euglycemic clamp procedure of up to 10 hours. Upon completion of the clamp procedures, the subjects will be provided a meal and observed overnight. Subjects will be discharged from the CRU the next day after medical assessments.

Study governance considerations are described in detail in Appendix 3 of the protocol.

[figure not shown]

Figure ITRT.1 illustrates the study design.

Treatment Sequence	Period 1	Period 2	Period 3	Period 4
1	LY900014 Abdomen	LY900014 Thigh	LY900014 Deltoid	LY900014 IV
2	LY900014 Deltoid	LY900014 Abdomen	LY900014 IV	LY900014 Thigh
3	LY900014 IV	LY900014 Deltoid	LY900014 Thigh	LY900014 Abdomen
4	LY900014 Thigh	LY900014 IV	LY900014 Abdomen	LY900014 Deltoid

Abbreviation: IV = intravenous.

Note: Subcutaneous injection sites are the abdomen, deltoid and thigh.

Figure ITRT.2 illustrates the treatment sequences.

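### IV is named as the reference for GD activity, but the GD inference in both documents covers only the three SC sites, so no SC/IV estimate of Gtot or Rmax is planned

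*SAP*

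**What the plan says.** **Role given to IV.** Protocol 3.1 says that IV administration "will serve as the reference to determine the absolute bioavailability of SC injections into the deltoid, thigh, or abdomen and GD activity". The synopsis rationale says the same.

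**Design.** Protocol 5.1 and SAP 5 describe the study as one "to compare the insulin lispro PK and GD of LY900014 after SC administration of a 15-U dose at 3 different injection sites and a single" (the sentence goes on to name the 15-U intravenous dose).

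**Objective.** The secondary GD objective in SAP 4.2 reads "To evaluate the GD during euglycemic clamp procedure of LY900014 after SC injection into the abdomen, thigh, and deltoid and IV in healthy subjects". Protocol Table ITRT.1 gives Gtot and Rmax as its endpoints.

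**Inference.** SAP 9.4.2 specifies "ratios of geometric LSmeans between injection sites (deltoid and thigh compared with the abdomen), and their corresponding 90% CIs" and states that "Data from the deltoid, thigh and abdomen injection sites will be included in the same model". It reuses the PK code of SAP 9.3.2, in which abdomen is the control level. The protocol synopsis and Protocol 10.3.3.2 name the same two contrasts.

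**What IV GD data do receive.** SAP 9.4.1 plans descriptive statistics by treatment group and mean LOESS profiles. SAP 6 lists IV as the fourth treatment in the tables. SAP 9.1 adds geometric mean and geometric CV for log-normal data, which may extend to Gtot and Rmax. An SC-to-IV ratio is planned only for insulin lispro AUC(0-∞) (Protocol 10.3.2.1, SAP 9.3.1).

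**The concern.** A reference implies that something is compared with it. If both plans are followed exactly, the report will hold IV and SC summaries of Gtot and Rmax side by side, but no estimate of how they differ within a subject and no interval.

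Side-by-side summaries are a weak substitute in this design. The GD population in SAP 8 needs only one completed clamp, and up to 28 subjects may be enrolled to obtain 22 completers, so as many as 28 − 22 = 6 may contribute incomplete data. IV falls in period 4, 3, 1 and 2 of sequences 1 to 4 (Table ITRT.2). A sequence 1 subject who leaves early contributes SC clamps but no IV clamp. Unadjusted treatment means can then come from different subjects and different mixes of periods, and they do not use the within-subject pairing that Protocol 5.4 gives as the reason for a crossover.

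**Working it through.** **Step 1. Set promise against analysis.**

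| Place | IV in GD? |
|---|---|
| Protocol synopsis rationale and 3.1 | Yes, as reference |
| Protocol synopsis design and 5.1; SAP 5 | Yes, within the comparison |
| Protocol Table ITRT.1; SAP 4.2 | Yes, within the objective |
| Protocol 10.3.3.1; SAP 9.4.1 | By treatment group: descriptive statistics and LOESS profiles |
| Protocol synopsis analysis and 10.3.3.2 | No IV contrast |
| SAP 9.4.2 | No IV contrast; only SC data named for the model |

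No section of either document specifies an SC/IV ratio of Gtot or Rmax.

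**Step 2. Reproduce the plan's own precision figure.** Inputs from Protocol 10.1 and SAP 7: n = 22 completers, intrasubject log SD 0.2 for AUC(0-∞), two-sided 90% CI, observed ratio 1.

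Half-width on the log scale = t(0.95, df) × SD × √(2/n), with √(2/22) = 0.3015.

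- Normal quantile: half-width 0.0992, CI 0.906 to 1.104.
- t on 21 df: half-width 0.1038, CI 0.901 to 1.109.
- Least-squares variance from the actual four sequences (6/6/5/5 completers, SC data only): variance factor 0.0912, df = 66 − 22 − 3 − 2 = 39, CI 0.903 to 1.107.

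All lie inside the stated range of about 0.8 to 1.25, so the stated figure holds. It concerns AUC at the SC sites and says nothing about GD.

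**Step 3. Apply the same formula to an SC/IV contrast.** With four treatments there are 4 × 22 = 88 observations. Removing 22 for subjects (which absorb sequence), 3 for periods and 3 for treatments leaves 88 − 22 − 3 − 3 = 60 df. From the actual sequences, the variance factor for an SC/IV contrast is 0.0911 to 0.0913, against 2/22 = 0.0909, so period adjustment costs almost nothing.

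The documents give no SD for Gtot or Rmax, so a range is assumed, with one residual variance common to IV and SC:

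| Assumed log SD | 90% CI at observed ratio 1 |
|---|---|
| 0.2 | 0.90 to 1.11 |
| 0.3 | 0.86 to 1.16 |
| 0.4 | 0.82 to 1.22 |
| 0.5 | 0.78 to 1.29 |

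Up to an SD of 0.4 the interval stays inside the 0.8 to 1.25 range that the plan uses for AUC. For any other observed ratio, multiply both limits by that ratio.

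**Step 4. Allow for unequal variances.** If the IV and SC residual SDs differ, the standard error is roughly √((SD_SC² + SD_IV²)/22), which reduces to SD × √(2/22) when they are equal. The df are then estimated rather than fixed at 60, so the intervals in step 3 are illustrations, not predictions.

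**The case against.** Four stronger readings are tempting, and the documents do not support them.

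- *The SAP departed from the protocol.* It did not. The protocol synopsis and 10.3.3.2 already restrict GD inference to deltoid and thigh against abdomen. The SAP's extra sentence only makes the exclusion of IV explicit, and on this point the no-changes statement in SAP 11 is correct. The mismatch lies between the rationale and design wording and the inference sections of both documents.
- *The secondary objective is not met.* Its verb is to evaluate, and its endpoints are Gtot and Rmax, not ratios. Where the protocol wanted an SC/IV ratio it said so, in the primary absolute bioavailability objective. Descriptive output can meet the GD objective as worded.
- *IV GD data go unanalysed, or get arithmetic means only.* They are summarized and profiled, and SAP 9.1 may bring in geometric summaries. The detailed table content is in a TFL shell document that is not part of the reviewed material.
- *The trial was meant to state what share of the IV glucose-lowering effect each site delivers.* Neither document says this. The rationale clause is loosely built and names no GD ratio, and the synopsis design summary ties the IV injection to absolute bioavailability. An Rmax ratio compares peak rates and could not measure a share of effect.

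It is also true that the IV clamp is not run solely for a GD contrast. The IV period is needed for the primary objective, and Protocol 3.3 cites the clamp among the measures that limit hypoglycemia risk. SAP 3 permits additional analyses if the CSR identifies them.

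What remains is that the words reference and compare are in the text, and nothing in the planned inference corresponds to them for IV. An analysis permitted later is not a prespecified one.

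**Conclusion.** The point holds as a gap between stated purpose and planned inference, present in both documents. Following the plan yields no model-based IV mean, no SC/IV ratio and no confidence interval for Gtot or Rmax. It affects a secondary objective; the primary AUC(0-∞) analyses and the planned GD site contrasts do not depend on it. It is a worthwhile low-cost improvement rather than an error that endangers the trial's conclusions.

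The precision shown rests on 22 completers, log-normal data, assumed SDs of 0.2 to 0.5 and a common residual variance. Only the completer number and the log-normal assumption come from the plan, and the plan states the latter for AUC.

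**What to change.** Keep the three-site model in SAP 9.4.2 for the site contrasts. Add a secondary mixed model with all four treatments: treatment, period and sequence fixed, subject within sequence random, and residual variance allowed to differ between IV and SC. Report geometric LSmeans for the four treatments and the three SC/IV ratios with 90% CIs. Make Gtot the main parameter, and present Rmax as a comparison of peak rate. Record the addition in SAP 11.

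If the sponsor prefers to leave IV GD descriptive, the alternative is to say so in SAP 9.4.2 and align the rationale and design wording with it.

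The model costs one more run and a few more table rows, with no new data and no change to the planned site contrasts.

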9.5 Safety and Tolerability Assessments

9.5.1 Adverse events

Where changes in severity are recorded in the Case Report Form (CRF), each separate severity of the adverse event (AE) will be reported in the listings, only the most severe will be used in the summary tables. A pre-existing condition is defined as an AE that starts before the subject has provided written informed consent and is ongoing at consent. A non-treatment emergent AE is defined as an AE which starts after informed consent but prior to dosing. A treatment-emergent AE is defined as an AE which occurs postdose or which is present prior to dosing and becomes more severe postdose.

All AEs will be listed. Treatment-emergent AEs will be summarized by injection site, severity and relationship to the study drug. The frequency (the number of AEs, the number of subjects experiencing an AE and the percentage of subjects experiencing an AE) of treatment-emergent

AEs will be summarized by treatment, Medical Dictionary for Regulatory Activities (MedDRA) version 19.1 system organ class and preferred term. The summary and frequency AE tables will be presented for all causalities and those considered related to the study drug. Any serious AEs will be tabulated.

9.5.2 Concomitant medication

Concomitant medication will be coded using the World Health Organisation (WHO) drug dictionary (Version September 2016). Concomitant medication will be listed.

9.5.3 Clinical laboratory parameters

All clinical chemistry, hematology and urinalysis data will be listed. Additionally clinical chemistry, hematology and urinalysis data outside the reference ranges will be listed.

Values for any clinical chemistry, hematology and urinalysis values outside the reference ranges will be flagged on the individual subject data listings.

9.5.4 Vital signs

Vital signs data will be listed for individual subjects. Vital signs data will be summarized by treatment.

9.5.5 Electrocardiogram (ECG)

ECG data is not databased for this study so will not be reported.

9.5.6 Injection Site Assessment

Injection site assessment data will be listed for individual subjects and will be summarized in frequency tables by treatment. This is collected during the non-IV treatment periods.

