## 2. Schedule of Activities

## Study Schedule of Protocol I8B-MC-ITRT

Procedures	Screening	Periods 1, 2, 3, 4			FU/ EDa	Comments
	Up to Day -28	Day -1	Day 1	Day 2		
Informed consent	X					
Admission to CRU		X				
Enrollment			X			Enrollment prior to taking first predose blood sample for the study.
Overnight fast	X	X				Subjects are expected to fast for approximately 8 hours before screening, and at least 8 hours before each dose until the end of the glucose clamp procedure.
Height	X					
Weight	X	X #			X	# Period 1 only
Hip and waist circumference		X #				# Period 1 only
Medical history and physical examination	X					
Medical assessment	X		Predose	X*	X	Medical assessment includes medical review and physical examination, as appropriate. *Prior to discharge from CRU for each period
Vital signs (supine): blood pressure and pulse rate	X		Predose, 1 hour postdose (IV period only), and 10 hours postdose (at the end of clamp procedure)		X	Predose vital signs may be collected up to 3 hours before dosing.
12-Lead ECG	X		Predose and 10 hours postdose (at the end of clamp procedure)		X	Single ECGs will be collected for safety. Predose ECGs may be collected up to 3 hours before dosing.
Clinical laboratory tests	X		Predose of Period 1. For IV period: 1 hour postdose		X	One hour postdose blood samples will be drawn only for the study period when LY900014 is administered intravenously.
Pregnancy test	X	X			X	For females of childbearing potential only. A serum pregnancy test will be performed at screening and urine pregnancy tests will be performed at all other time points.

Procedures	Screening	Periods 1, 2, 3, 4			FU/ EDA	Comments
		Up to Day -28	Day -1	Day 1		
Study drug administration				0 hour		Time of study drug administration = 0 hour. Study drug will be administered at approximately the same time on Day 1 of each study period. The site of administration will be determined by the randomization schedule.
Injection-site assessments				0, 1, 4, and 10 hours postdose		Time 0: assessments will occur immediately following the injection.
Insulin lispro PK sampling				2.5, 5, 10, 15, 20, 25, 30, 40, 60, 70, 90, 120, 150, 180, 210, 240, 300, 360, 420, 480, 540, and 600 minutes		Sampling times are relative to the time of study drug administration (time 0).

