**Table ITRT.1. Objectives and Endpoints**

Objectives	Endpoints
Primary To determine the relative bioavailability of insulin lispro from LY900014 after SC injection into the thigh and deltoid compared to the abdomen in healthy subjects.	AUC(0-∞)
To determine absolute bioavailability of insulin lispro following SC administrations of LY900014 into the thigh, deltoid, and abdomen compared to IV administration of LY900014 in healthy subjects.	Percent of the ratio of AUC(0-∞)
Secondary To evaluate the tolerability of LY900014 in healthy subjects.	Adverse events and injection-site reactions
To evaluate the GD during euglycemic clamp procedure of LY900014 after SC injection into the abdomen, thigh, and deltoid and IV in healthy subjects.	$G_{tot}$ and $R_{max}$
Exploratory Objectives To evaluate C-peptide levels after administration of LY900014.	C-peptide concentrations
To determine plasma concentrations of the excipient, treprostinil, following administration of a single, IV 15-U dose of LY900014 in healthy subjects.	Plasma concentrations–over-time profile

Abbreviations: AUC(0-∞) = area under the concentration versus time curve from time zero to infinity; GD = glucodynamics;  $G_{tot}$  = total amount of glucose infused; IV = intravenous;  $R_{max}$  = maximum glucose infusion rate; SC = subcutaneous.

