## 5. Study Design

### 5.1. Overall Design

This is a Phase 1, single-center, open-label, 4-period, randomized, crossover, up to 10-hour euglycemic clamp study in approximately 28 healthy subjects to compare the insulin lispro PK and GD of LY900014 after SC administration of a 15-U dose at 3 different injection sites and a single IV bolus injection of 15 U. The SC injection sites are the abdomen, thigh, and deltoid.

Subjects will be required to attend the clinical research unit (CRU) on at least 6 occasions:

[figure not shown]
- screening visit (may occur up to 28 days before randomization)
- four treatment visits for the clamp procedure (study Periods 1 to 4) with a wash-out period of  $\geq 3$  days between discharge and the next admission to the CRU
- follow-up visit (at least 14 days after last dose), or early discontinuation.

Each subject will be randomly assigned to a treatment sequence and will be administered single doses of 15 U of LY900014 (on 4 occasions).

Subjects will be admitted to the CRU on the evening before each dosing day and will remain in the CRU for the duration of the clamp period and until discharge by the investigator. Subjects are expected to fast for at least 8 hours before each dose. Following dose administration, each subject will undergo an euglycemic clamp procedure of up to 10 hours. Upon completion of the clamp procedures, the subjects will be provided a meal and observed overnight. Subjects will be discharged from the CRU the next day after medical assessments.

Study governance considerations are described in detail in [Appendix 3](#).

[Figure ITRT.1](#) illustrates the study design and [Table ITRT.2](#) presents the treatment sequences.

Abbreviations: CRU = clinical research unit; IV = intravenous; SC = subcutaneous.

\*Single dose of LY900014 administered either SC in the abdomen, thigh, deltoid or IV. Up to 10-hour euglycemic clamp procedure after each dose.

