### 7.2. Method of Treatment Assignment

The injection site where LY900014 is to be injected on a given treatment day will be determined according to a randomization schedule.

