#### ***9.4.6. Injection-Site Assessments (Local Tolerability)***

Injection-site assessments for local tolerability will be conducted as specified in the Schedule of Activities (Section 2) and more frequently if deemed necessary by the investigator.

Digital pictures will be taken, if possible, of the injection site at the time of identification of local intolerance and thereafter as often as judged necessary by the investigator. The pictures should include subject number, visit number, time after dosing, and a ruler for scaling.

Local tolerability at the injection site will be evaluated by means of assessments within the following categories: pain on palpation, itching, erythema, edema, and induration/infiltration.

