6. TREATMENTS

The following is a list of the study treatment names that will be used in the TFLs.

Study Treatment Name	Treatment order in TFL
15 U LY900014 Abdomen	1
15 U LY900014 Thigh	2
15 U LY900014 Deltoid	3
15 U LY900014 IV	4

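### Does the SAP wrongly leave the IV period out of the injection-site assessments?

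*SAP*

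**What the plan says.** Protocol section 9.4.6 names the local tolerability categories (pain on palpation, itching, erythema, edema, induration/infiltration) and leaves the timing to the Schedule of Activities. The Schedule puts the assessments at "0, 1, 4, and 10 hours postdose" on Day 1, under the block for Periods 1 to 4. The row's only comment explains time 0.

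SAP section 9.5.6 lists these data by subject and summarizes them in frequency tables by treatment, then adds: "This is collected during the non-IV treatment periods". SAP section 6 gives four treatment names for the tables, the fourth being "15 U LY900014 IV".

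In Table ITRT.1 the tolerability objective is secondary, with the endpoint "Adverse events and injection-site reactions".

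**The concern.** The Schedule marks exceptions where it means them. Its vital-signs row reads "Predose, 1 hour postdose (IV period only), and 10 hours postdose (at the end of clamp procedure", treprostinil sampling and the 1-hour laboratory tests are also limited to the IV period, and hip and waist circumference is limited to Period 1. An unmarked row therefore looks deliberate, and a site following it would examine the IV site as well. The SAP says otherwise, and its section 11 reports no changes from the protocol's analyses.

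If the case report form followed the SAP sentence while the protocol intended all four treatments, the structured local assessments for one of four treatments would be missing from a secondary endpoint that carries no route limit. If instead the site recorded IV-period assessments, the SAP does not say whether the by-treatment table should include them.

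**Working it through.** The plan gives no figure to reproduce on this point. The check is a count, a comparison of wording, and a look at what the report would lose.

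**Count of assessments in doubt.** Inputs: 4 time points per period (Schedule); 4 periods (Schedule) or 3 non-IV periods (SAP 9.5.6); 22 completers and at most 28 enrolled (Protocol 10.1).

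- Schedule read literally: 4 × 4 = 16 per subject. SAP: 4 × 3 = 12. Difference: 4, and 4/16 = 25%.
- 22 completers: 22 × 16 = 352 against 22 × 12 = 264, a difference of 88.
- 28 subjects, all completing: 28 × 16 = 448 against 28 × 12 = 336, a difference of 112.

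These are ceilings. They apply only if all four treatments were meant to be assessed and the IV data were not collected or tabulated.

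**What the protocol means by injection site.** Pointing to the subcutaneous sites only:

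- Protocol 5.1 describes dosing at "3 different injection sites and a single IV bolus injection of 15 U", so the IV dose is counted apart from the sites. The Synopsis is built the same way.
- Protocol 7.1 speaks of different injection sites for the subcutaneous doses and names the IV dose separately. Table ITRT.3 gives the route as a subcutaneous injection or an IV bolus.
- Protocol 7.2.1 describes the IV dose as a push through a cannula followed by a saline flush.
- In Protocol 10.3.2.2 and SAP 9.3.2, injection site is the model factor. The contrasts are deltoid and thigh against abdomen, and the SAP says that data from these three sites enter the model.

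Pointing to all four treatments:

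- Protocol 7.2 says: "The injection site where LY900014 is to be injected on a given treatment day will be determined according to a randomization schedule". That schedule includes the IV dose.
- The Synopsis calls the IV dose an injection into the forearm.
- SAP 9.5.1 summarizes treatment-emergent adverse events by injection site, which presumably covers the IV period too.

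The usage is not uniform, but the design, treatment and analysis sections lean clearly towards the subcutaneous sites. The Schedule's own dosing row uses a different term, site of administration, for the randomized assignment.

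**What the report would lose.** Suppose the SAP is followed exactly as written.

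- IV-period treatment-emergent adverse events are still summarized by treatment (SAP 9.5.1), so a local reaction reported as an adverse event appears there.
- Anything entered in the database is listed (SAP 9.1), including any IV-site assessments the site records.
- Safety has no inferential analysis (SAP 9.5.9). Protocol 10.3.1.2 says only that these parameters will be listed and may be summarized, so no table required by the protocol has been dropped.
- The relative and absolute bioavailability analyses do not use these data.

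**The case for a change.** The strongest case for a change is that intent has to be inferred. Protocol 9.4.6 hands the matter to the Schedule, and the Schedule has no route limit where neighboring rows do. Where Protocol 7.2.1 means the subcutaneous sites it says so explicitly, which suggests that the unqualified term could be wider. The SAP's precedence clause (section 3) covers statistical considerations, not which procedures are performed, so the SAP sentence cannot by itself switch off a scheduled assessment. A finding on structured examination that was too mild to be reported as an adverse event could then go untabulated for the IV treatment.

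Of this, the mismatch in wording stands: no protocol passage says that the assessment is for subcutaneous periods only. The rest carries less weight.

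- The SAP sentence gives the reason for an absent IV column, so a reader would not be left guessing.
- A general list of treatment names in SAP section 6 does not oblige every table to have four columns.
- SAP section 11 speaks of changes to statistical analyses. Which periods collect an assessment is a matter of data collection, so that statement need not be false.
- Whether any IV-site data are captured or tabulated depends on the case report form and the separate table shells, which are not among the documents. No loss of data has been shown.

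**Conclusion.** The two documents do differ in wording. This is a missing annotation on one Schedule row, not a fault in the analysis plan. The most likely reading is that local tolerability was meant for the three subcutaneous sites and that the SAP says so explicitly. On that reading nothing is lost.

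On the less likely reading, at most 25% of scheduled assessments (88 of 352 for 22 completers, 112 of 448 for 28) would be missing from one descriptive table. Adverse events would still be tabulated for the IV treatment, and any recorded data would still be listed. No estimate, interval or study conclusion would move on either reading.

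This rests on two assumptions: that the predominant usage of the term reflects intent, and that local reactions in the IV period are recorded as adverse events when they occur, as Protocol 9.2 requires for adverse events generally. An analyst can handle the point by naming the covered treatments in the table title. Annotating the row would be harmless tidying with no demonstrated gain.
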